The primary hypothesis is that children in TEAM-ED will have more symptom-free days at 3, 6, 9, and 12-months compared to eUC. Previous asthma interventions have demonstrated that improvements of 0.85-0.95 SFD/2 weeks are feasible and clinically meaningful.^{59,60} Based on our prior data, we estimate a pooled standard deviation (SD) of SFD to be 3.5 and within-subject correlation (ICC) of 0.3. We calculated power for the intervention effect on SFD while justifying repeated assessments for outcomes (3, 6, 9, 12 months).^{61,62} A sample size of 182 subjects per group will provide >90% power to detect a difference of 0.85 in SFD at a 2-sided 5% significance level.⁶³ We also calculated the smallest detectable differences in secondary outcomes with 80% power based on prior data.

We also aim to test whether children in TEAM-ED will have fewer unscheduled asthma visits over 12 months compared to eUC. Based on our preliminary data and data for similar populations, we estimate the baseline unscheduled asthma visit rate ranges 0.7-1.5 per person year. A sample size of 365 subjects will provide 80% power to detect a rate ratio of 0.7 if the control group has rate of 0.7 per person year. For preventive measures such as preventive medication use, in our prior study, 59% of children used a preventive medication at baseline. With 182 subjects in each group, we will have 90% power to detect an increase of 16% in using a two-sided Z test at a significance of 5%.

Primary Analysis:

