Assess the effectiveness of TEAM-ED in reducing asthma morbidity and preventing repeat unscheduled asthma visits; Assess the effectiveness of the intervention in improving preventive asthma care. We will follow subjects prospectively throughout the year for clinical outcomes (symptoms, asthma control, health care use), functional outcomes (absenteeism, quality of life), and airway inflammation (FeNO). We will use graphs and descriptive statistics to summarize the primary and secondary outcomes by intervention group at each assessment point (baseline, 3, 6, 9 and 12 months). We will assess for differences between groups at baseline despite randomization in key characteristics (i.e.; age, race, ethnicity, insurance, caregiver education, caregiver depression, smoke exposure (determined by cotinine)). These comparisons will enable the identification of covariates to be controlled when evaluating the treatment effect. If distributional assumptions associated with a particular statistical procedure are violated, appropriate transformations will be made or non-parametric alternatives will be used. In accordance with the intention-to-treat principle,⁶⁴ all randomized subjects will be analyzed within the group to which they were assigned. Minimal crossover is expected. Hypothesis-driven comparisons will be made to control the family-wise type I error rate at 0.05 (two-sided) for the primary hypothesis.

For the primary outcome analysis, the time-course of treatment effect on SFD during the follow-up period will be evaluated using a linear mixed model (LMM) accounting for repeated measures within each subject to test the intervention effect of TEAM-ED over time, with SFD as the dependent variable, and intervention group and group by time interaction as independent variables.⁶⁵ The treatment effect will be regarded as fixed and the subjects as the random effect, with appropriate variance covariance structure specified. Interaction effects between intervention and follow-up period are included to catch possible differences in how SFD changes over time between intervention groups. Post treatment effects and maintenance gain from short to long term will be assessed by specifying appropriate linear contrasts. To adjust for potential confounding, baseline SFD and factors that differentiate between

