groups will be included in the model as covariates. Model fitting statistics such as Information Criteria and difference in log likelihood will be used for model selection. Standard measures such as residual plots will check goodness-of-fit of the regression model assumptions and identify outliers. We will calculate intraclass coefficient (ICC) within providers; if autocorrelation is significant, provider will be included as another level of random effect in the mixed model to account for the nested data structure. If the outcome measure violates the normal assumption required by LMM, we will evaluate the intervention effect using Generalized Estimating Equations (GEE).⁶⁶ By specifying marginal mean effects of independent variables on the outcome variable, the GEE method offers consistent and robust estimates but does not require specification of a fully parametric distribution. Other continuous outcomes (quality of life, FeNO, absenteeism) will be analyzed similarly.

Categorical outcomes such as unscheduled asthma-related healthcare utilization will be analyzed by fitting Poisson regression models (with number of visits as the dependent variable). Estimation of the regression coefficients and standard errors will be obtained using the GEE method with a log link function and Poisson error. Baseline rate and factors imbalanced between groups will be controlled in this analysis. Other discrete outcomes (such as preventive medication use and availability of written asthma action plans) will be analyzed in a similar manner with appropriate link functions and response probability distributions specified.

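### The primary SFD analysis names no deciding contrast and leaves model choice to the data, so 0.05 control is not assured and the effect tested may not be the one powered

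*Combined protocol and SAP*

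**What the plan says.** The Primary Analysis section describes the main analysis as the time-course of the treatment effect on SFD. It uses a linear mixed model (LMM) with group and group-by-time terms, a subject random effect, and baseline SFD as a covariate. Linear contrasts are mentioned but not written out. Several parts are left open:

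- **Model form:** "Model fitting statistics such as Information Criteria and difference in log likelihood will be used for model selection".
- **Distribution, for SFD:** "If the outcome measure violates the normal assumption required by LMM, we will evaluate the intervention effect using Generalized Estimating Equations".
- **Distribution, in general:** if the assumptions of a procedure fail, "appropriate transformations will be made or non-parametric alternatives will be used".
- **Other parts:** the covariance structure is to be whatever is appropriate, covariates are those found to differ at baseline, and a provider random effect is added if it proves significant.

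On error control the same section says: "Hypothesis-driven comparisons will be made to control the family-wise type I error rate at 0.05 (two-sided) for the primary hypothesis". It names no test, contrast or multiplicity procedure.

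The Sample Size section gives the hypothesis as more SFD at 3, 6, 9 and 12 months, without saying whether this means on average, at every visit or at any visit. The Cost Effectiveness Analysis section calls the primary outcome mean SFD over 12 months.

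**The concern.** The model-selection sentence comes straight after the group, interaction and covariate terms, and nothing confines it to the covariance structure. One permitted reading is that the group-by-time term is kept or dropped on the trial data and that the test then depends on the result. That is a pre-test, and it can raise the error rate above the promised 0.05.

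The second difficulty does not depend on how selection is done. The text supports several primary tests: an average over visits, a joint test, a difference at one visit, or the interaction. They answer different questions and have very different power, and only one of them can match the sample size calculation. A transformation or rank method would also leave the scale of days on which the 0.85 difference is defined.

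**Working it through.** **Inputs, all from Sample Size.** 182 per group; difference 0.85 SFD per 2 weeks; four follow-up assessments; test "at a 2-sided 5% significance level". For the variance, "we estimate a pooled standard deviation (SD) of SFD to be 3.5 and within-subject correlation (ICC) of 0.3".

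**1. The plan's own figure.** The claim is: "A sample size of 182 subjects per group will provide >90% power to detect a difference of 0.85 in SFD".

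- Averaged over four visits: effective SD = 3.5 × √((1 + 3 × 0.3)/4) = 2.412. SE = 2.412 × √(2/182) = 0.253. 0.85/0.253 = 3.36. Power = Φ(3.36 − 1.96) = 91.9%.
- At a single visit: SE = 3.5 × √(2/182) = 0.367. 0.85/0.367 = 2.317. Power = Φ(2.317 − 1.96) = 63.9%.

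Only the averaged difference gives more than 90%.

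**2. Power of the other tests the text allows**, with a constant 0.85 effect and the same inputs. The joint test uses a noncentral chi-square with noncentrality 3.361² = 11.30.

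| Test | Power |
|---|---|
| Time-averaged difference | 91.9% |
| Joint 4-df test over visits | 77.5% |
| One visit, for example the group coefficient with month 3 as reference | 63.9% |
| One visit at 0.05/4 | 42.8% |
| 3-df group-by-time interaction | 5.0% (equal to alpha) |

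The ranking depends on the constant effect. If the effect faded in a straight line from 1.70 to 0 with the same average, the joint test would have 99.6% power and month 12 only 5%. The averaged contrast would stay at 91.9%.

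**3. Type I error if selection decides which effect is tested.** Simulation under no effect: 2,000,000 draws, complete data, compound symmetry, correlation 0.3. The time-averaged contrast is tested if the interaction is dropped. If it is kept, the test is the one in the left column. The rules are assumed.

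| Test after the interaction is kept | Kept by 5% likelihood-ratio test | Kept by AIC |
|---|---|---|
| Month 12 only | 5.8% | 6.3% |
| Four visits, Bonferroni | 6.3% | 6.9% |
| Joint 4-df test | 8.1% | 8.4% |
| Any of four visits, unadjusted | 8.4% | 10.9% |
| Time-averaged contrast regardless | 5.0% | 5.0% |

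Letting AIC choose among no, linear and categorical interaction, with the matching joint test, gives 9.8%; BIC over the same set gives 6.4%. Reading any unadjusted visit with no selection at all gives 17.4%.

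The mechanism shows in the joint-test row. Trials where the interaction is dropped contribute 0.95 × 0.05 = 4.75%. The remaining 8.1 − 4.75 = 3.35 percentage points come from the 5% of trials where it is kept, so about two thirds of those reject. With the averaged contrast always tested nothing is added, because under compound symmetry that contrast is independent of the interaction statistic.

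**4. Type I error if selection touches only nuisance parts** and the averaged contrast is kept.

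- Covariance chosen by AIC from compound symmetry, AR(1) and unstructured: 4.78% under compound symmetry, 5.42% under an assumed decaying correlation (0.42, 0.28, 0.15), and 5.45% with data rounded and bounded to 0–14. Each used 6,000 trials, so the simulation error is √(0.05 × 0.95/6000) = 0.28 percentage points.
- Covariates chosen by baseline p < 0.05 (seven, each assumed to correlate 0.2 with the outcome): 3.9%.

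**5. Non-normality.** SFD per 2 weeks lies between 0 and 14, so some departure from normality is predictable. With an assumed distribution that puts 46% of values at 14, comparing mean SFD still gave 5.2% error over 20,000 trials. A comparison of means does not need the switch at this sample size.

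**The case against.** The strongest reply is that the interaction is written into the model and nothing says it may be dropped. Information criteria and likelihood differences are ordinary tools for choosing a covariance structure or deciding on a provider effect, and both are left open nearby. On that reading error stays near 5%. This is as natural a reading as the other, but the sentence does not state its scope, and even on this reading the deciding contrast is missing.

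A reader might infer that the plan as written breaches 0.05, and cite 8.4% or 10.9%. The documents do not support that. Those figures need two assumptions: that the interaction can be dropped, and that any of four unadjusted visits then counts as success. The second conflicts with the plan's commitment to family-wise control and by itself gives 17.4% without any selection.

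A reader might also blame the move from LMM to GEE. With an identity link and the same mean model, GEE estimates the same mean difference. In 20,000 simulated trials of complete bounded data (distribution assumed), error was 4.9% with model-based standard errors, 5.1% with robust ones, and 5.1% if either rejection counted. Nor is reliance on missing completely at random left unaddressed: the plan specifies weighted GEE if data are missing at random. The option that could change the estimand is transformation or a non-parametric method. That sentence is generic, and GEE is the fallback given specifically for SFD, so its use for SFD is possible rather than stated. No formal normality test is planned either; the section names residual plots.

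**Conclusion.** The point holds in a limited form. The plan leaves the primary SFD analysis to data-driven choices and names no deciding contrast. Control at 0.05 is therefore not assured, which is weaker than saying it is lost.

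The firmest part is the mismatch with the power calculation: 91.9% for the averaged difference against 77.5%, 63.9% or 5% for other tests the text permits. It rests on the plan's own inputs and a constant effect. The type I error figures are conditional: about 6% to 8% under simple keep-or-drop rules, 9.8% if AIC may also pick a linear interaction, and up to 11% if any unadjusted visit counts. All of them rest on decision rules that the plan does not state, with complete data and compound symmetry. Missing data and provider clustering were not simulated. The point should be settled before unblinding; it does not undermine the design or the sample size.

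**What to change.** In the Primary Analysis section:

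1. Name one primary contrast: the TEAM-ED minus eUC difference in untransformed SFD, averaged over 3, 6, 9 and 12 months, tested at two-sided 0.05. Visit-specific differences and the interaction become secondary.
2. Fix the mean model in advance: arm, categorical visit, arm-by-visit, baseline SFD, and the two randomization strata (enrollment site and baseline preventive medication use).
3. Limit fit statistics to nuisance parts such as the covariance structure, or use robust standard errors. An unstructured covariance is one acceptable choice, not a requirement.
4. For SFD, make transformed, non-parametric, GEE, weighted GEE and bounded-outcome analyses sensitivity analyses.

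The change is to wording. With the averaged contrast fixed, power is 91.9% and type I error 5.0% (complete data, compound symmetry), so the sample size stays as it is. The cost is a few extra model parameters and less freedom for the analyst.

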There may be some cost to participate in this study. Participants in the TEAM- ED group will be responsible to purchase medications and spacers that may be prescribed by the telemedicine provider as well as any fees associated with telemedicine visits (e.g., co-pays etc.) completed through the study (these are medical processes that should occur according to the national guidelines regardless of the child's participation in the study). Based on our prior work with this population, we anticipate that most of the children will have some form of health insurance to cover the cost of visits and the medications with minimal or no co-pay fee. In our prior studies we found that approximately 70% of families in the City of Rochester were insured with Medicaid which often eliminates co-pay fees for medications and care. If a child does not have insurance, the study team will help the family secure health insurance. If a child is unable to obtain health insurance or if a family or provider expresses a financial concern, the study team will pay for the participant's asthma medication and spacer prescribed by the telemedicine provider. If there is no insurance reimbursement for the telemedicine visit, subjects will not be asked to pay any additional costs (e.g., co-pay). Participants and their insurance company will be responsible for the cost of all standard of care office visits and additional medications prescribed by their PCP.

- **Data Storage and Confidentiality**

To maintain the integrity, security, and confidentiality of study data, the data will be maintained in a secure and encrypted web-based database and/or a password protected database on a secure university network drive. The majority of data will be entered through REDCap™, a secure password-protected website supported by the University of Rochester. Subject tracking information will also be entered into a secure password-protected database created with Microsoft Access, that is only accessible on a secure university network drive and research personnel must use their University NetID and password to access the databases. No subject data will be stored on the internal hard drives of any computers. After data validation and analysis, subject information will be de-identified. All consent forms, paper surveys and additional correspondence will be stored in a locked filing cabinet in a locked hallway or locked office, and will only be accessible by the study staff.

- **Safety**

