The primary analyses will be performed according to the intention-to-treat principle and will include all randomized subjects. Substantial attention will be invested in participant retention; reasons for any subject withdrawals that may occur will be carefully documented. Missing data patterns will be examined by comparing subjects who discontinued with those who remained in the study. Inference based on the proposed methods GEE and/or LMM is valid provided that missing data follows the missing completely at random (MCAR) assumption. However, if the occurrence of missing data depends on the observed response but is independent of unobserved data (MAR), weight GEE (WGEE) will be used. Sensitivity analysis to the MAR assumption will also be carried out by modeling the between-group difference using WGEE.^{67,68} Separate secondary per protocol analyses will be performed, however, results of these analyses are potentially subject to bias and will be interpreted with appropriate caution.

Cost Effectiveness Analysis: *Establish the financial sustainability of the intervention with a specific focus on ultimate dissemination.* We will assess the health and economic benefits of TEAM-ED from both the societal and the Medicaid perspectives. We also will use Diffusion of Innovations Theory to help understand how this innovative model can be maintained in the current system of care.

We will use cost-effectiveness (CE) methodology^{69,70} to assess the health and economic benefits of TEAM-ED versus eUC over 12 months. The basecase analysis will be conducted from the societal perspective which includes all identifiable costs and benefits, regardless of whom they impact. Since the majority of subjects are eligible for Medicaid (73% based on prior work⁵⁹), a second analysis will take the Medicaid perspective. The intervention benefits will be assessed using the primary outcome (mean symptom-free days over 12 mos.).^{71,72}

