Three main categories of costs to be considered include programmatic costs, productivity costs, and medical costs estimated at the individual child level. Programmatic costs include costs of initiating and running the program, hiring and training staff, purchasing or leasing equipment, staff travel, and information system costs. Programmatic costs will be tracked by the UR General Pediatric Division Administrator and the UR Telemedicine Program Administrator. Research-related costs that are not associated with the intervention and would not exist beyond the duration of the study will not be

included. Per person programmatic costs will be calculated by dividing the total costs of the program by the total number of children with persistent asthma in the EDs. We will determine productivity costs based on the amount of time parents take from work to care for sick children or take them to a doctor. Time from work will be valued at the median of the Bureau of Labor Statistics pay scale estimates based on age, race and gender. We will assess the impact of the intervention on medical costs using both parent-reported health care utilization data and medical record review. We will ask parents at each follow-up about their child's visits to the ED, urgent care facility, or primary care office, as well as hospitalizations. Health care use will be converted to costs using the NYS Medicaid fee schedule and other sources. Money spent out-of-pocket by caregivers to cover the cost of medical procedures, medications, or equipment will also be included in the medical costs. Annual medical costs per person will be analyzed using a 2-part model to adjust for zero expenses in a given year.⁷³ All costs will be adjusted to the last year of the intervention using the appropriate component of the Consumer Price Index (CPI).

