We will consider the total cost of initiating and maintaining the program as well as the incremental cost-effectiveness ratio (ICER) of TEAM-ED versus eUC. The ICER is the difference in cost between the 2 study groups relative to the difference in the number of symptom-free days (SFD) gained between the 2 groups. The main outcome for the analysis from the societal perspective will be the ICER, defined as: $(\Delta Medical + \Delta Productivity + \$Program) / \Delta SFD$, where $\Delta = (TEAM-ED) - (eUC)$. We will bootstrap⁷⁴ the ICER to estimate standard error and to evaluate the uncertainty around the point estimate. The ICER will be compared to similar estimates from the literature.^{71,72} An acceptability curve, linking various values of 1 SFD to the probability of TEAM-ED being cost-effective, will be plotted.⁷⁵ The study from the Medicaid perspective will use the cost-benefit approach to economic evaluation. Benefits will be described as the net difference in medical and productivity costs between children in the TEAM-ED and eUC groups and accounts for a potential reduction in unplanned visits as well as an increase in number of preventive visits. The cost is equivalent to the cost of the program ($Net Monetary Benefit = \Delta Medical - \$Program$).

COVID-19

In response to the COVID-19 crisis, we will follow the Human Subjects Research guidelines outlined by the University of Rochester to continue enrollment for this study. Please find the following link for these guidelines: <https://www.urmc.rochester.edu/coronavirus/coronavirus-research/guidance-for-researchers/human-subjects-research.aspx>. We will minimize in-person contacts to only those tasks necessary to conduct the research (e.g., obtaining consent, collecting breathing measurements if needed). We will ensure that team members are appropriately trained in safety measures, maintain social distancing when possible, use personal protective equipment for themselves and research subjects (and family members), and will ensure proper cleaning/sanitizing of hands, equipment and workstations. We will continue to monitor and follow the updated guidelines put forth by the UofR in the link above.

We've included a brief, optional survey to assess how the COVID-19 Crisis is affecting children with asthma and their families. We will ask the caregivers if they would be willing to answer these questions at the end of follow-up surveys that we are already conducting.

References

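### The Medicaid net monetary benefit reuses a medical-cost total that includes caregivers' out-of-pocket payments, which Medicaid does not pay

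*Combined protocol and SAP*

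**What the plan says.** The relevant text is in the Cost Effectiveness Analysis part of the Analysis section.

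- **Perspectives.** The base case takes the "societal perspective which includes all identifiable costs and benefits, regardless of whom they impact". Because most subjects are expected to be eligible for Medicaid (73%, from prior work), "a second analysis will take the Medicaid perspective".
- **Medical costs.** On health care use: "We will ask parents at each follow-up about their child's visits to the ED, urgent care facility, or primary care office, as well as hospitalizations". On valuation: "Health care use will be converted to costs using the NYS Medicaid fee schedule and other sources". On family spending: "Money spent out-of-pocket by caregivers to cover the cost of medical procedures, medications, or equipment will also be included in the medical costs".
- **Formulas.** The societal ICER divides the sum of the medical-cost difference, the productivity-cost difference and the program cost by the difference in symptom-free days. For the payer, "The study from the Medicaid perspective will use the cost-benefit approach to economic evaluation", with "Net Monetary Benefit = \Delta Medical - \$Program". The medical term carries the same symbol in both formulas.

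The Compensation section says that TEAM-ED families are responsible for prescribed medications and spacers, "as well as any fees associated with telemedicine visits (e.g., co-pays etc.) completed through the study". It also expects most children to have insurance that leaves little or nothing to pay, and says that Medicaid frequently removes co-pays.

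**The concern.** A payer-perspective analysis should contain only the payer's money. Money a caregiver spends is, by definition, not spent by Medicaid. The plan puts that money into medical costs and then carries the same medical-cost difference into the Medicaid formula without removing it.

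The cost aim is to establish financial sustainability with a view to dissemination. The Medicaid result is the figure a payer would read to judge what the program costs or saves it. If it includes family spending, it does not answer that question.

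A second, weaker issue concerns the societal ICER. The plan states no rule for setting out-of-pocket payments against fee-based values, so a visit co-pay might be counted once inside the fee and again as family spending.

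**Working it through.** The plan states no co-pay, unit cost, cost difference or ICER, so there is no figure to reproduce. The check uses accounting identities.

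**Definitions** (between-arm differences per child, TEAM-ED minus eUC):
- F = value assigned to health care use from the fee schedule and other sources
- C = co-pays on that same care
- O = out-of-pocket spending on items with no fee value

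**As written.** Medical difference = F + C + O, used in both formulas.

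**What each perspective should hold.** This depends on whether fee values include the patient's share (gross) or are the payer's payment only (net). The plan does not say which.

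| | Gross | Net |
|---|---|---|
| Societal, correct | F + O | F + C + O |
| Societal, excess as written | C | 0 |
| Medicaid, correct | F − C | F |
| Medicaid, excess as written | 2C + O | C + O |

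**Illustration.** The values are assumed and are not from the documents; F = 100 throughout.

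| C | O | As written | Societal excess, gross / net | Medicaid excess, gross / net |
|---|---|---|---|---|
| 0 | 0 | 100 | 0 / 0 | 0 / 0 |
| 0 | 20 | 120 | 0 / 0 | 20 / 20 |
| 5 | 0 | 105 | 5 / 0 | 10 / 5 |
| 5 | 20 | 125 | 5 / 0 | 30 / 25 |
| 20 | 20 | 140 | 20 / 0 | 60 / 40 |

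The Medicaid term is wrong under both readings whenever out-of-pocket spending differs between arms, unless C and O happen to cancel. The societal term is wrong only under the gross reading, and only if co-pays differ between arms. If eUC families pay more, C is negative and the error reverses: C = −5 with O = 0 gives a Medicaid error of −10 (gross) or −5 (net).

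**Scale of the co-pay part.** The documents put the Medicaid share at about 70% (Compensation), 73% (Cost Effectiveness Analysis) and 75% (Background). Assume co-pays are zero under Medicaid, and assume a between-arm co-pay difference of $5, $20 or $50 per non-Medicaid child, in either direction. Multiplying by 0.25 to 0.30 gives an average over the sample of $1.25–$1.50, $5.00–$6.00 or $12.50–$15.00 per child. These figures give the size of C only. Nothing in the documents allows O to be estimated.

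**Cost of restricting to Medicaid-covered children.** 0.73 × 365 ≈ 266 children. With similar variance the interval widens by 1/√0.73 = 1.17, or about 17%.

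**The case against.** The strongest reply concerns the societal ICER, where a reader might infer that co-pays are double counted. The documents do not show that. They do not say that visits are valued at a full fee including the patient's share. The listed health care use is visits and hospitalizations, while medications and equipment are named only under out-of-pocket spending, so the two sentences can be read as complementary. The societal perspective covers costs whoever bears them, so family spending belongs there once. This reply stands: the societal issue is only an unstated netting rule.

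A reader might also infer that TEAM-ED is overcharged, since its families may meet telemedicine co-pays. That does not follow either. eUC families are prompted to make primary care visits, which may carry co-pays, and any ED visits avoided in TEAM-ED would offset more. The Compensation section adds that families are not asked to pay when a telemedicine visit is not reimbursed, and that the study covers telemedicine-prescribed asthma medication and spacers where coverage cannot be obtained or cost is a concern. The sign is unknown.

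On the Medicaid formula, one could argue that an analyst would drop family payments without being told. The text gives no sign of this. The sentence introducing the formula describes the benefits as including productivity costs, which are not Medicaid outlays either, and no second medical-cost variable is defined.

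**Conclusion.** The point holds for the Medicaid perspective. Followed as written, the plan places caregiver payments in a result meant to represent Medicaid's money. This rests on two explicit statements, the content of medical costs and the reuse of one medical-cost term, and on no assumption about fees. The amount and direction cannot be determined from the documents. The effect is probably small, given the co-pays the plan itself expects, and it touches a secondary economic analysis, not the primary outcome.

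For the societal ICER the plan needs clarification. Double counting is possible only if fee values are gross of the patient's share.

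A reader might conclude that the Medicaid analysis must exclude children outside Medicaid. The documents do not require that. The plan does not state the population for this analysis, and applying Medicaid fees to all children is a defensible way to model a Medicaid population. Restriction is a trade-off against precision.

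**What to change.** 1. Define a separate payer-only medical cost, containing Medicaid-paid items and excluding caregiver out-of-pocket payments, and use its between-arm difference in the Medicaid net monetary benefit.
2. Keep out-of-pocket spending in the societal ICER only.
3. State, for the fee schedule and for each other source, whether values are gross or net of the patient's share. Add to the societal cost only out-of-pocket amounts not already in those values. This step must come first: dropping visit co-pays when values are net would understate the societal cost.
4. State which children enter the Medicaid analysis. A version limited to Medicaid-covered children can be an optional sensitivity analysis.

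The cost is some SAP wording and one additional cost variable. Out-of-pocket amounts need to be recorded so that payments on fee-valued care can be told apart from other items. The optional restriction would widen the interval by the 17% shown above, if coverage is 73% and variance is similar.
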